10.4 Vital Signs

Blood pressure, heart rate, respiratory rate, and oral temperature will be measured at screening, Day -1 of each period and at study exit. Blood pressure and pulse rate will be measured at pre-dose, and at 2 hours post-dose in each period.

Individual results and reference ranges will be presented in a data listing. For each vital sign measurement, observed values and changes from baseline for quantitative test results will be summarized by treatment or overall, as appropriate, for each timepoint using descriptive statistics. Baseline will be defined for each vital sign measurement as the last results (scheduled or unscheduled) obtained prior to study drug administration in each period. Unscheduled results will not be used in the summary tables except for baseline if applicable.

10.5 12-lead Electrocardiograms

Standard 12-lead ECGs will be recorded at screening, on Day -1 of each period, and at study exit.

Individual results and change from baseline will be presented in a data listing. Baseline will be defined for each ECG parameter as the last results (scheduled or unscheduled) obtained prior to first study drug administration. Abnormal results will be flagged, as applicable.

10.6 Sheehan Suicidality Tracking Scale (S-STS)

The S-STS will be administered at screening and at study exit. Individual total scores with change from baseline will be presented in a data listing.

This document is confidential.

11 PHARMACOKINETIC ANALYSES

11.1 Below the Lower Limit of Quantification and the No Reportable Concentration

Plasma concentrations will be listed and summarized, by nominal sampling time, and treatment. Concentrations below the quantification limit (BLQ) will be set to zero for calculation of PK parameters and in summary tables. Samples with invalid concentration (due to bioanalytical issue) will be replaced by “0.00” when it occurs prior to dosing. Otherwise they will be set to missing for tabulation, graphical representation, and calculation purposes if it occurs after dosing. BLQ will be displayed in listings. For geometric mean calculations for PK parameters involving zero values, zero values will be substituted with 0.0001.

For individual plots, the BLQ values will be set to zero. For mean plots, BLQ will be set to zero.

11.2 Difference between the Scheduled and the Actual Sampling Times

The actual clock time for dosing and the actual clock time for each collection time for the PK samples will be recorded using electronic data capture. For all sampling times, the actual sampling times will be calculated as the difference between the actual clock time of sample collection and the actual clock time of dosing. The actual post-dose sampling times expressed in hours and rounded off to three decimal digits will be used to calculate the PK parameters, except for pre-dose samples occurring prior to dosing, which will always be reported as zero (0.000), regardless of the time difference. Scheduled nominal sampling times will be presented in concentration tables and mean graphs, while actual sampling times will be presented in the individual graphs in the PK section of the report. Actual sampling times also will be used for final PK parameter derivation. If actual sampling time is missing, then nominal time will be used. A listing of the actual times for PK sampling will be provided for PK samples.

This document is confidential.

11.3 PK Parameters

Blood samples will be collected for zavegeptan PK analysis at pre-dose (within 1 hour prior to dosing), and 0.25, 0.5, 1, 1.5, 2, 2.5, 3, 4, 5, 6, 8, 10, 12, 16, and 24 hours post-dose in each period. Bioanalysis of all associated plasma samples should be completed prior to the initiation of the PK and statistical analyses. Analysis will be performed using a fully-validated analytical method by a qualified bioanalytical laboratory.

The following PK parameters will be calculated, based on the PK population, by standard non-compartmental methods using the plasma concentrations of zavegeptan.

Parameter	Definition
AUC _{last}	area under the concentration-time curve from time zero until the last observed concentration
AUC _{inf}	area under the concentration-time curve from time zero to infinity (extrapolated)
AUC _{extrap%}	percentage of AUC _{0-inf} due to extrapolation from the time of the last observed concentration to infinity, calculated as $[1 - (AUC_{last}/AUC_{inf})] \times 100$
C _{max}	maximal observed concentration
T _{max}	time when the maximal concentration is observed
T _{1/2}	terminal elimination half-life
K _{el}	terminal elimination rate constant
CL/F	apparent clearance
V _z /F	apparent volume of distribution

PK of Treatment C (AUCs and C_{max}) will be normalized to a dose of 100 mg.

Additional PK parameters may be calculated.

Note: AUC parameters will be calculated using linear up log down trapezoidal method, where the linear trapezoidal rule is used any time the concentration data is increasing, and the logarithmic trapezoidal rule is used any time that the concentration data is decreasing.

Note: K_{el} will be the negative of the estimated slope of the ln-transformed concentration versus time profile in the terminal elimination phase. The best fit method, in Phoenix WinNonlin, will be used to calculate the K_{el} from at least three concentration data points, excluding C_{max}. Rsq (R-squared) adjusted, the goodness of fit statistic for the terminal elimination phase, adjusted for the number of points used in the estimation of K_{el} must be ≥ 0.9 . If the K_{el} cannot be measured (e.g.: there are fewer than three non-zero concentrations in the terminal elimination phase or Rsq adjusted < 0.9), the PK parameters derived from K_{el} (AUC_{inf}, AUC_{extrap%}, T_{1/2}, CL/F, V_z/F) will be presented in listing with a flag and excluded from descriptive statistics and statistical analyses. The timepoint where ln-linear K_{el} calculation begins (K_{el} Lower) and the actual sampling time of the last measurable concentration used to estimate the K_{el} (K_{el} Upper), as well as the Rsq adjusted for the ln-linear regression for the calculation of the elimination rate constant will be reported.

This document is confidential.

If the $AUC_{extrap\%}$ is more than 20%, the individual result should be flagged as well as all parameters depending on AUC_{inf} . All the derived parameters (i.e., AUC_{inf} , $AUC_{extrap\%}$, $T_{1/2}$, CL/F, V_z/F) will be flagged accordingly, and they will be removed from the analyses and the descriptive statistics.

Some PK parameters may not be calculated for all participants, at the discretion of the Syneos pharmacokineticist with Sponsor agreement if the concentration data is not deemed to be amenable to evaluation. Explanations for PK parameters that could not be estimated will be provided in the report.

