8.3 Pharmacokinetic Parameters

The following PK parameters will be calculated based on the PK population by standard non-compartmental methods for zavegeptan.

- AUC_{0-t} : Area under the concentration-time curve from time zero until the last observed concentration
- AUC_{0-inf} : Area under the concentration-time curve from time zero to infinity (extrapolated)
- Residual area: Percentage of AUC_{0-inf} due to extrapolation from the time of the last observed concentration to infinity, calculated as $[1 - (AUC_{0-t}/AUC_{0-inf})] \times 100$
- C_{max} : Maximal observed concentration
- T_{max} : Time when the maximal concentration is observed
- $T_{1/2 el}$: Terminal elimination half-life
- K_{el} : Terminal elimination rate constant
- Cl/F : Apparent clearance
- V_z/F : Apparent volume of distribution

PK of Treatment C will be normalized to a dose of 100 mg.

Additional PK parameters may be calculated.

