3.3 Treatment Administration

Randomization schedules will be generated through SAS® for Windows software, prior to study execution. Participants enrolled in this study will be assigned to ACBD, CDAB, BADC, or DBCA sequences using a blocked randomization.

On Day 1 of each period, participants will receive a single oral dose of one of the following oral treatments, under fasting conditions, according to the assigned sequence on the randomization schedule.

Treatment	Description
A (Test 1)	1 x 100 mg zavegeptan non-enteric coated SGC (Biohaven Pharmaceuticals Holding Company Limited) administered under fasting conditions.
B (Test 2)	1 x 100 mg zavegeptan IR tablet + DDM dosage form (Biohaven Pharmaceuticals Holding Company Limited) administered under fasting conditions.
C (Test 3)	1 x 200 mg zavegeptan IR tablet (total dose of 200 mg) + DDM dosage form. The dose for Treatment C may instead be administered as 2 x 100 mg IR tablets + DDM dosage form for a total zavegeptan dose of 200 mg (Biohaven Pharmaceuticals Holding Company Limited) administered under fasting conditions.
D (Reference)	4 x 25 mg zavegeptan enteric coated SGC (total dose of 100 mg) (Biohaven Pharmaceuticals Holding Company Limited) administered under fasting conditions.

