5 PHARMACOKINETIC AND SAFETY PARAMETERS

For PK analyses, AUC_{last} , AUC_{inf} , and C_{max} calculated using zavegepant concentration data will be the primary endpoints. $AUC_{extrap\%}$, T_{max} , $T_{1/2}$, K_{el} , V_z/F and CL/F for zavegepant will be secondary endpoints; reference [section 11.3](#).

Safety and tolerability parameters are secondary endpoints; reference [section 10](#).

This document is confidential.

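### Halving the 200 mg arm's AUClast can overstate C/D if the 100 mg reference drops below the assay limit before 24 h while Treatment C is still measurable

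*SAP*

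**What the plan says.** - **Endpoint.** SAP section 5 makes AUClast, AUCinf and Cmax primary: zavegepant "concentration data will be the primary endpoints". SAP 11.3 defines AUClast as the "area under the concentration-time curve from time zero until the last observed concentration". No common end time is set.
- **Assay floor.** SAP 11.1: "Concentrations below the quantification limit (BLQ) will be set to zero for calculation of PK parameters and in summary tables". The rule is the same for every treatment.
- **Doses.** SAP 3.3 gives Treatment C as "1 x 200 mg zavegeptan IR tablet (total dose of 200 mg) + DDM dosage form", or alternatively two 100 mg tablets, and Treatment D as "4 x 25 mg zavegeptan enteric coated SGC (total dose of 100 mg").
- **Normalisation.** Protocol 8.3: "PK of Treatment C will be normalized to a dose of 100 mg". SAP 11.3 narrows this: "PK of Treatment C (AUCs and C_{max}) will be normalized to a dose of 100 mg".
- **Sampling.** SAP 11.3 samples at "0.25, 0.5, 1, 1.5, 2, 2.5, 3, 4, 5, 6, 8, 10, 12, 16, and 24 hours post-dose in each period", so the last intervals are 12 to 16 h and 16 to 24 h.
- **Comparison.** SAP 11.4.2 commits to a C/D geometric mean ratio with 90% CI for each primary parameter.
- **AUCinf.** SAP 11.3 removes AUCinf and its dependent parameters, including AUCextrap% itself, when extrapolation exceeds 20%. AUClast is not on that list.

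**The concern.** At twice the dose with the same kinetics, C's curve stays above a fixed assay limit about one half-life longer than D's. The area lost below the limit is roughly LLOQ/Kel for both doses in absolute terms, so it is about half as large a share of C's AUC. Dividing C's AUClast by 2 leaves that difference in place.

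This is not dose non-linearity and not a formulation effect. It would appear if the same product were given at two doses with perfectly proportional exposure. With proportional kinetics it can only favour Test 3. A/D and B/D compare equal doses and carry no such systematic shift. At stake is one of the three primary C/D ratios, the one meant to describe extent of absorption without extrapolation.

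**Working it through.** **1. The plan's own precision figure (SAP 3.4: CV 40%, ratio 1.0, 52 participants, CI width about 0.25).**
- Log-scale SD = sqrt(ln(1 + 0.40²)) = 0.385.
- Log half-width = t(0.95; 150 df) × 0.385 × sqrt(2/52) = 0.125.
- Limits exp(±0.125) = 0.8825 and 1.1332; width 0.251. The stated 0.25 reproduces, which gives a scale for the bias.

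**2. Closed form.** Let fD and fC be the shares of AUCinf lying beyond the last measurable sample. With identical absorption and linear kinetics, C/D for AUClast = (1 − fC)/(1 − fD). If the lost area is equal in absolute terms, fC = fD/2:

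| fD | (1 − fD/2)/(1 − fD) |
|---|---|
| 5% | 0.975/0.95 = 1.026 |
| 10% | 0.95/0.90 = 1.056 |
| 15% | 0.925/0.85 = 1.088 |
| 20% | 0.90/0.80 = 1.125 |

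This form treats sampling as continuous. The actual schedule does not behave that smoothly.

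**3. The SAP sampling times, without noise.** Assumptions: one-compartment oral model, ka 1/h, half-life 2 to 12 h, LLOQ 0.5% to 20% of the reference Cmax, C exactly twice D, linear-up/log-down AUC, C divided by 2. This gives 30 scenarios.
- In 22 of 30, C and D share the same last measurable sample and C/D is exactly 1.000.
- In the other 8, C/D runs from 1.02 to 1.19. It is never below 1.
- At half-life 6 h the effect comes and goes with the schedule:
  - LLOQ 5%: both curves end at 24 h; ratio 1.000.
  - LLOQ 10%: D ends at 16 h (fD 17.8%), C at 24 h (fC 7.1%); ratio (1 − 0.071)/(1 − 0.178) = 1.13.
  - LLOQ 20%: both end at 16 h; ratio 1.000.
- Cutting both AUCs at the reference's last measurable sample gives 1.0000 in all 30. AUCinf, before any removals, gives 1.000 to 1.002.

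**4. Average over a simulated population.** Variation between participants smooths the jumps. Over assumed half-lives of 3 to 8 h:

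| LLOQ, % of 100 mg Cmax | Average inflation of AUClast C/D |
|---|---|
| 2 or less | about 0–1% |
| 5 | about 0.5–3% |
| 10 | about 3–5% |
| 15 | about 8–9% |

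A second simulation with other population assumptions (half-life 4 to 8 h) gave 1.000–1.012 at an LLOQ of 2% or less, 1.007–1.030 at 5% and 1.037–1.059 at 10%.

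**5. AUCinf as a check.** In that second simulation, at half-life 6 h, the 20% rule removed 3.4% of D profiles against 0.9% of C profiles at LLOQ 5%. At LLOQ 10% it removed 18.8% against 3.4%.

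**The case against.** The strongest reply is that nothing shows this trial is affected. The effect needs D to fall below the limit before 24 h and C to be measurable at a later sample. The LLOQ and half-life are not given, and the assay is described elsewhere. There is also a hint of a sensitive assay: protocol 8.2.3 and SAP 6.5 allow exclusion when a pre-dose value exceeds 5% of Cmax, a threshold that is useful only if the assay can measure below it. That is an inference, but it points to the lower rows of the table. All of this stands, and it makes the point conditional.

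A reader might go further than the documents allow in three ways:
- **That halving always inflates C/D.** It does not. The effect is nil whenever both curves end at the same sample, including whenever both are measurable at 24 h.
- **That AUCinf is lost exactly where it is needed.** Removal requires more than 20% extrapolation, so at truncated shares of 5% to 20% AUCinf stays unless the Kel fit fails. It weakens only at a high LLOQ, where D is removed more often than C.
- **That a floor-adjusted AUClast should replace the planned one as the basis for concluding on C.** Setting C's quantified values to BLQ would conflict with SAP section 12 (reported concentrations are to be used) and section 14 (observed data only). The documents also set no acceptance limit against which such a conclusion would be drawn.

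Some diagnostics are already planned: AUCextrap% is a secondary endpoint and Kel Upper is reported. But AUCextrap% values above 20% leave the descriptive statistics, and Kel Upper is tied to the Kel fit. SAP 11.3 allows additional PK parameters but commits to none, and one chosen after C/D is known would carry less weight.

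Finally, the AUClast definition refers to the last observed, not the last measurable, concentration. Measurable is the usual reading. If the first BLQ zero were included, the noise-free range would shrink to 1.00–1.08 but not vanish.

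**Conclusion.** The point holds in conditional form. Under proportional kinetics, the plan's AUClast C/D ratio can be pushed up and not down, and no pre-specified analysis compares the two doses over the same stretch of curve. The likely size runs from nothing to a few per cent, reaching 8–9% only if the LLOQ is about 15% of the 100 mg Cmax. Against planned confidence limits of about 0.88 to 1.13 at a ratio of 1.0, the lower rows are minor and the top row is not.

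These figures rest on an assumed half-life, LLOQ and absorption model, and on reading the last observed concentration as the last measurable one. The documents cannot show whether the condition will occur. The point concerns AUClast for C/D alone: Cmax and the sample size are untouched. It is a cheap improvement to the plan, not a flaw that invalidates the comparison.

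**What to change.** In SAP 11.3 and 11.4.2:

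1. Keep AUClast and its C/D ratio as planned, and state that it ends at the last measurable concentration.
2. Pre-specify a sensitivity C/D ratio with 90% CI, using AUC from zero to a common time within participant: the earlier of that participant's C and D last measurable times, with C normalised to 100 mg. Defining the common time by scheduled sample, and integrating on actual times, avoids mismatches of a few minutes.
3. Report the time of last measurable concentration and AUCextrap% by treatment, before the removals above 20%, and state the LLOQ.
4. Interpret the AUClast C/D ratio alongside the sensitivity ratio.

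The cost is SAP wording and one derived parameter from existing data. Part of the measurable tail, mostly C's, goes unused in that ratio, and a participant needs both a C and a D profile to contribute. If C and D end at the same sample throughout, the within-participant comparison is unchanged.

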11.4 Statistical Analyses

Statistical analysis described in this section will be based on the PK statistical population.

11.4.1 *PK Parameters in Plasma*

Individual, mean and median plasma concentration versus time curves will be presented for both linear and semi-log scales. Descriptive statistics (arithmetic and geometric means, SD, CV%, geometric mean CV%, Min, Max, and median) of the plasma concentrations versus time will be presented as well for the PK parameters.

11.4.2 *Treatment Comparisons*

For zavegepant, using the MIXED procedure in SAS, an ANOVA will be performed on ln-transformed (dose-normalized to 100 mg) AUC_{last} , AUC_{inf} , and C_{max} . No adjustments will be made to alpha for multiple pairwise comparisons. As the study was dosed in more than one Group, the following terms will be included in the statistical model: Group, Sequence, Sequence by Group, Period within Group, Treatment, and Treatment by Group. A random effect of Participant within Sequence by Group will also be included. In case of a non-statistically significant Treatment by Group interaction term, the analysis will be rerun excluding this term from the ANOVA model in order to obtain ratios and confidence intervals where appropriate. The ratio of geometric means and 90% confidence intervals (A/D), (B/D), and (C/D) based on least-squares means from the ANOVA of the ln-transformed data will be calculated for AUC_{last} , AUC_{inf} , and C_{max} . The point estimates and confidence intervals will be exponentiated using base e in order to obtain a point and interval estimate for the ratio of geometric means. Other ratio of geometric means among treatments may be explored. Untransformed T_{max} will also be analyzed using the MIXED model with the difference of least-squares means from the ANOVA calculated for (A-D), (B-D), and (C-D). Other differences of least-square means between treatments may be explored. The K_{el} , and $T_{1/2}$ will be summarized descriptively.

The SAS code to fit the model will follow the format below (using the Mixed Procedure). The input variables, datasets, and labels are depicted in italicized red text and have been given generic names.

This document is confidential.

```
proc mixed data = basepk;
  class Group Sequence Period Treatment Participant;
  model VAR = Group Sequence Sequence*Group Period(Group) Treatment
    Treatment*Group / ddfm = kenwardroger;
  random Participant (Sequence*Group);
  lsmeans Treatment;

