12 PERCENTAGES AND DECIMAL PLACES

Percentages:

Percentages based on count data should be displayed as follows in TLFs:

- $0 < \text{percentage} < 0.1$ as “<0.1”
- $99.9 < \text{percentage} < 100$ as “>99.9”
- 100 percentage as “100”
- 0 count without a percentage in frequency tables
- Rounded to 1 decimal place otherwise.

For response rates (proportions), measures of variability such as standard error (SE) and confidence interval (CI) should be displayed rounded to 1 decimal place.

Continuous Variables Non-PK Data:

Descriptive statistics for continuous variables in tables should be displayed as follows:

- Values and changes from baseline
 - Minimum and maximum: same precision as the data collected or rounded to a specified precision if derived
 - Mean and percentiles: rounded to 1 decimal place more than the data collected or derived
 - Measure of variability (e.g., standard deviation [SD], SE, CI): rounded to 2 decimal places more than the data collected or derived
- Percent change from baseline
 - Minimum and maximum: rounded to 0 decimal places (i.e., integers)
 - Mean and percentiles: rounded to 1 decimal place
 - Measure of variability: rounded to 2 decimal places.

Individual data in listings should be displayed to the same precision as the data collected or rounded to a specified precision if derived.

Derived variables should be calculated using all precision from collected components. For example, BMI should be derived as needed using all precision from collected height and weight. However, the specified precision for reporting BMI should be 1 decimal place.

Continuous Variables PK Data:

Concentration data for parameter calculations: The concentration data as reported by the respective bioanalytical groups should be used, without rounding, for all analyses.

This document is confidential.

Concentration data listings: By default, concentration values should be presented in listings exactly as reported by the respective bioanalytical groups. However, in cases when concentration data may be supplied electronically with unrealistic precision, rounded values may be presented. A default of 3 significant figures is suggested, and the rounding used should be described in the clinical study report.

Parameter data listings: The non-compartmental parameters should not be reported to any greater precision than that of the concentration data. A default of 3 significant figures is preferred.

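### The 20% extrapolation rule in SAP 11.3 caps the AUCextrap% summary at 20% and drops T1/2 from fits whose Kel is kept

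*SAP*

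**What the plan says.** SAP 11.3 has two exclusion rules, one after the other.

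- **Kel rule.** Kel needs three or more concentrations, not counting Cmax, and an adjusted R-squared of at least 0.9. If it cannot be measured, the parameters derived from it (AUCinf, AUCextrap%, T1/2, CL/F, Vz/F) "will be presented in listing with a flag and excluded from descriptive statistics and statistical analyses".
- **20% rule.** If AUCextrap% is above 20%, "the individual result should be flagged as well as all parameters depending on" AUCinf. The next sentence repeats the same five parameters and says they "will be flagged accordingly, and they will be removed from the analyses and the descriptive statistics". Kel is not on the list.

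The parameter table in SAP 11.3 defines AUCextrap% as the percentage of AUCinf "due to extrapolation from the time of the last observed concentration to infinity, calculated as" [1 − (AUClast/AUCinf)] × 100. SAP 11.4.1 summarises the PK parameters by "arithmetic and geometric means, SD, CV%, geometric mean CV%, Min, Max, and median". SAP 11.4.2 plans descriptive summaries of Kel and T1/2 side by side. SAP 5 makes both AUCextrap% and T1/2 secondary endpoints. Protocol 8.3 and 8.4 define the residual area and the Kel and T1/2 summaries without any 20% cut-off.

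**The concern.** The 20% rule is introduced for quantities that depend on AUCinf, but its list is the one from the Kel rule. Two entries cause trouble.

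**AUCextrap%.** It does depend on AUCinf, so it meets the stated criterion. But removing it when it is large truncates the summary on the very quantity being summarised. A reader uses this row to judge whether sampling to 24 h was long enough, and the rule takes out the values that would show it was not.

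**T1/2.** It is a function of Kel alone and does not meet the rule's criterion. It is dropped from fits that have already passed the Kel rule. Longer half-lives tend to leave larger extrapolated tails, so the removed values tend to be the long ones and the summarised T1/2 tends to be too short. Kel from the same fits stays, so two adjacent rows describe different sets of profiles and need not agree.

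**Working it through.** The plan gives no figure of its own on this point, so the check is a reading of the rules followed by an illustration with assumed inputs.

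**1. What follows from the text alone**

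- CL/F and Vz/F are computed from AUCinf, and AUCextrap% is defined by it. The SAP prints no formula for T1/2. The standard relation is T1/2 = ln 2 / Kel, and the SAP's own Kel rule classes T1/2 as derived from Kel.
- Every AUCextrap% left in the summary is at most 20%. Hence its Max is at most 20%, and its mean falls whenever a value is removed.
- n(T1/2) = n(Kel) − (profiles with an acceptable Kel and AUCextrap% above 20%). One such profile makes the two sets differ.
- No other section of either document puts these values back into a summary.

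**2. When the rule starts to act**

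For a mono-exponential profile still quantifiable at 24 h, the extrapolated fraction is exp(−Kel × 24). Setting this to 0.20 gives T1/2 = ln 2 × 24 / ln 5 = 10.3 h. With one-compartment first-order absorption the threshold is 9.4, 9.9 and 10.1 h at ka = 0.5, 1 and 2 per hour. Between-profile spread, or a last quantifiable sample before 24 h, triggers it at shorter typical half-lives.

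**3. Illustration**

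*From the documents:* planned sampling times to 24 h, linear-up/log-down AUC, best-fit Kel under the SAP criteria, BLQ set to zero, 52 subjects.

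*Assumed:* typical T1/2 as in the table; LLOQ 2% of typical Cmax; ka 1 per hour (CV 30%); exposure CV 50% between and 40% within subjects. Low variability is T1/2 CV 20% with assay error 5%; high is 30% with 10%.

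Each scenario used 5,200 profiles, cut into about 100 trials of 52 accepted fits. Values are medians over trials, shown low / high.

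| Typical T1/2 | Removed of 52 | Median T1/2, all → kept (h) | Max AUCextrap%, all → kept |
|---|---|---|---|
| 4 h | 0 / 0 | unchanged | – |
| 6 h | 0 / 2 | 5.95→5.95 / 5.88→5.77 | 18→17 / 26→19 |
| 8 h | 8 / 12 | 7.92→7.64 / 7.77→7.15 | 29→20 / 37→20 |
| 10 h | 26 / 24 | 9.90→8.61 / 9.58→7.96 | 38→20 / 46→20 |

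- The chance that at least one profile is removed is 0% / 8% at 4 h and 33% / 89% at 6 h.
- At 8 h the fall in median T1/2 is 1 − 7.64/7.92 = 3.5% (low) and 1 − 7.15/7.77 = 8.0% (high). The Kel row would still imply 7.92 and 7.77 h.
- Repeating the 8 h case on the same assumptions again removed about 8 / 12 profiles, with median T1/2 7.98→7.68 / 7.88→7.17 h.
- With LLOQ at 10% of Cmax the cap already acts at 4 h: 5 / 7 removed and maximum AUCextrap% 35→20 / 36→19. Median T1/2 moves only 1–2%.

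**4. A second set of assumptions**

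This used a wider half-life spread (SD of log 0.35), ka around 1.5 per hour, no assay error, and LLOQ 2–10% of median Cmax. T1/2 was kept for 94.7–99.6% of Kel-estimable profiles at 4 h, 84.2–93.1% at 6 h and 65.4–74.2% at 8 h. At 8 h the geometric mean T1/2 was about 6.9 h under the rule, against about 8.0 h from ln 2 / geometric mean Kel. Mean AUCextrap% was 10.7–13.8% under the rule, against 15.0–18.2% on all profiles.

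**The case against.** The best defence is that a large extrapolated tail marks a weakly supported terminal phase, so dropping T1/2 may be deliberate. The first simulation gives this some support: at LLOQ 2%, the Kel fits of removed profiles spanned about 1.2–1.4 half-lives, against 1.8–3.2 for those retained. But this is an argument about fit quality. It applies equally to the Kel from which T1/2 is computed, and the SAP keeps that Kel.

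Other points stand, and they limit the harm:

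- Because T1/2 = ln 2 / Kel, a reader can recover the full-set geometric mean, minimum and maximum of T1/2 from the Kel row, apart from rounding, and the median almost exactly.
- AUCextrap% is not the only evidence on sampling length. The SAP also provides flags on individual results, the start, end and adjusted R-squared of each Kel fit, concentration summaries at 24 h, and semi-log curves.
- Flagged values would probably still appear in the parameter listings that SAP 12 provides for. Table shells are in a separate document and might include a count.
- The two sets of assumptions give different sizes. At 8 h and LLOQ 2% the first removes 15–23% of profiles (8/52 to 12/52) and the second 26%. No single figure should be relied on.

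None of this restores the truncated AUCextrap% summary, or explains why T1/2 and Kel from one fit are treated differently.

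**Conclusion.** The concern holds and is minor. Once any profile with an acceptable Kel exceeds 20%, it is certain from the text that the AUCextrap% maximum is capped at 20% and that T1/2 is summarised on fewer profiles than Kel. If no profile exceeds 20%, nothing changes.

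The size is not determinable from the documents and depends on the assumed half-life, its spread and the LLOQ. With a low LLOQ it is nil or near nil at 4 h or less, modest at 6 h and larger from 8 h. The affected endpoints are secondary and descriptive. The A/D, B/D and C/D ratios for AUClast and Cmax are unaffected. Removal of AUCinf, CL/F and Vz/F above 20% is not disputed here.

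**What to change.** In SAP 11.3:

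1. Delete T1/2 and AUCextrap% from the 20% removal list. Keep the rule for AUCinf, CL/F and Vz/F.
2. Summarise T1/2 and AUCextrap%, with flags, on every profile that meets the Kel criteria, so that both share the denominator of Kel.
3. Report the number of profiles with AUCextrap% above 20% by treatment.

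If the sponsor considers short-tail fits too weak for a T1/2 summary, state that as a fit criterion and apply it to Kel as well. A sensitivity analysis of AUCinf that retains the flagged profiles is optional.

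The cost is two list entries deleted and one count row added to a table. No model and no primary analysis changes.
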